1. PROTOCOL SYNOPSIS FOR STUDY 201097

Rationale

Current levels of asthma control in China fall short of the goals specified in international guidelines for asthma management (GINA). A nationwide multi-centre epidemiologic survey performed by China Asthma Alliance also showed that only 28.7% of the patients with asthma in China achieved complete asthma control. There is a large gap between what can be achieved with modern asthma management and what is currently being achieved. One of the main reasons for this is a lack of recognition of asthma control and the requirement for more effective treatment. Physicians can select appropriate treatment regimen only after they identify those patients with uncontrolled asthma. Simple methods aiming to improve the assessment of asthma control have been developed. The Asthma Control Test (ACT) is a validated, short, easy to use, and self-administered instrument used to assess asthma control. However, physicians do not use it, even though it was designed to assess the level of asthma control in patients and so guide physicians treatment decisions. This study is aimed at evaluating the effectiveness of ACT guided treatment compared with usual care in asthma patients in China. It is designed to assist Chinese patients and physicians improving adherence to the guidelines through the inclusion of the ACT in the patient's asthma management plan.

Objective(s)/Endpoint(s)

Objectives	Endpoints
Primary	

 To compare the effectiveness of ACT guided treatment versus usual care in achieving asthma control 	
 the percentage of subjects who have an ACT score ≥ 20 or an improvement of more than 3 points in ACT during the 24-week treatment period
Secondary	

 To compare the effectiveness of ACT guided treatment versus usual care in asthma subjects with respect to the following parameters: 
 Symptoms Forced Expiratory Volume in one second (FEV1) Peak Expiratory Flow(PEF) The quality of life Time to asthma control 	
 Mean daytime symptom score over the 24-week treatment period Mean night-time symptom score over the 24-week treatment period Mean change from baseline to the end of study in FEV1 Mean morning(AM) PEF over the 24-week treatment period Mean evening(PM) PEF over the 24-week treatment period Mean change from baseline to the end of study in Standardised Asthma Quality of Life Questionnaire (AQLQ[S]) score Time to first ACT score ≥ 20 or improvement of more than 3 points in ACT over the 24-week treatment period
Others	

 To compare the effectiveness of ACT guided treatment versus usual care in asthma exacerbation 	
 Rate of moderate/severe asthma exacerbation over the 24-week treatment period

Overall Design

This is a prospective, multicentre, cluster-randomised, open-label study.

Treatment Arms and Duration

The study is planned to be a 24-week study.

Baseline (week 0, visit 0): ACT, AQLQ(S) and lung function test will be completed as the baseline measurement in sequence.

Treatment period (week 0-week 24): a 24 week treatment period. Subsequent scheduled visits occur as follows: Week 4 (Visit 1), Week 8 (Visit 2), Week 12 (Visit 3), Week 16 (Visit 4), Week 20 (Visit 5) and Week 24 (Visit 6).

In this cluster-randomization design, each study centre, considered as a cluster, will be randomized to either ACT guided treatment group or control group (usual care group). The randomization will be stratified according to the hospital level (Tier 3 vs. Tier 2). The hospital level is determined in accordance with the uniform requirements of the government. A Tier 3 hospital is on a larger scale and provides superior medical care than a Tier 2 hospital.

For the subjects who are recruited in the ACT centres, they will be treated based on the ACT score. For subjects who are recruited in the control centres, they will be treated based on doctor's subjective judgment.

ACT score	Treatment adjustment
ACT=25, ≥ 3 months	Step-down treatment
ACT ≥ 20 , <25 or ACT=25, <3 months	No change
ACT ≤ 19	Step-up treatment

Type and Number of Subjects

A total of 528 subjects are required in a total of 12 centres (6 centres per group) and around 44 asthma subjects per centre.

Analysis

The null hypothesis for this study is that there is no difference between ACT guided treatment and usual care in the percentage of subjects who have an ACT score ≥ 20 or an improvement of more than 3 points in ACT during the 24-week treatment period for the intention-to-treat (ITT) population.

The alternative hypothesis for this study is that there is a difference between ACT guided treatment and usual care in the percentage of subjects who have an ACT score ≥ 20 or an improvement of more than 3 points in ACT during the 24-week treatment period for the ITT population.

The primary endpoints will be analyzed using logistic regression. The statistical model on which the inference will be based will include terms for treatment, centre, type of baseline controller (inhaled corticosteroids [ICS] alone vs. ICS/long-acting β 2 agonist [LABA]), gender and age. Centre, as the unit of randomization, will be treated as a random effect. The results of the primary analyses will be presented as point estimates, 95% confidence intervals and associated p-values for the adjusted mean differences between ACT guided treatment and usual care.

2. INTRODUCTION

2.1. Study Rationale

Current levels of asthma control in China fall short of the goals specified in international guidelines for asthma management (GINA). A nationwide multi-centre epidemiologic survey performed by China Asthma Alliance also showed that only 28.7% of the patients with asthma in China achieved complete asthma control [Nan, 2013]. There is a major gap between what can be achieved with modern asthma management and what is currently being achieved. One of the main reasons for this is a lack of recognition of asthma control and the requirement for more effective treatment. Physicians can select appropriate treatment regimen only after they identify those patients with uncontrolled asthma. Simple methods aiming to improve the assessment of asthma control have been developed. The asthma control test (ACT) is a validated, short, easy to use, and self-administered instrument used to assess asthma control [Nathan, 2004]. However, physicians do not use it, even though it was designed to assess the level of asthma control in patients and so guide physicians treatment decisions. This study is aimed to evaluate the effectiveness of ACT guided treatment compared with usual care in asthma patients in China. It is designed to assist Chinese patients and physicians improving adherence to the guidelines through the inclusion of the ACT in the patient's asthma management plan.

2.2. Brief Background

GINA has adopted a five-step approach to control asthma, where each step represents a different treatment option with increasing efficacy [GINA, 2013]. The five-step approach provides treatment options to achieve and maintain control, with the least amount of medication. Asthma control assessment is very important to assess what is the appropriate treatment for the patient. In a questionnaire survey in Canada, primary care physicians were given questionnaires to guide them through control assessments. They were also asked to indicate whether or not they considered the patient's asthma to be under control. It was found that physicians significantly overestimated control among their patients and were discordant with guideline classification of control as 31% of the patients were assessed as uncontrolled patients, 13% were well-controlled and 2% were totally controlled [Chapman, 2008]. In China, poor physician:patient dialogue has made the situation worse. During busy clinical practice, physicians often make management

[figure not shown]
decisions based on their subjective perceived level of asthma control. This potentially leads to under-treatment and consequently sub-optimal asthma control.

3. OBJECTIVE(S) AND ENDPOINT(S)

Objectives	Endpoints
Primary	

 • To compare the effectiveness of ACT guided treatment versus usual care in achieving asthma control 	
 • the percentage of subjects who have an ACT score ≥ 20 or an improvement of more than 3 points in ACT during the 24-week treatment period
Secondary	

 • To compare the effectiveness of ACT guided treatment versus usual care in asthma subjects with respect to the following parameters: 
 • Symptoms • Forced Expiratory Volume in one second (FEV1) • Peak Expiratory Flow(PEF) • The quality of life • Time to asthma control 	
 • Mean daytime symptom score over the 24-week treatment period • Mean night-time symptom score over the 24-week treatment period • Mean change from baseline to the end of study in FEV1 • Mean morning (AM) PEF over the 24-week treatment period • Mean evening (PM) PEF over the 24-week treatment period • Mean change from baseline to the end of study in Standardised Asthma Quality of Life Questionnaire (AQLQ(S)) score • Time to first ACT score ≥ 20 or improvement of more than 3 points in ACT over the 24-week treatment period
Others	

 • To compare the effectiveness of ACT guided treatment versus usual care in asthma exacerbation 	
 • Rate of moderate/severe asthma exacerbation over the 24-week treatment period

4. STUDY DESIGN

4.1. Overall Design

This is a prospective, multicentre, cluster-randomized, open-label study.

Protocol waivers or exemptions are not allowed with the exception of immediate safety concerns. Therefore, adherence to the study design requirements, including those specified in the Time and Events Table, are essential and required for study conduct.

4.2. Treatment Arms and Duration

- The study is planned to be a 24-week study.
- Baseline (week 0, visit 0): Subjects eligible for inclusion criteria will sign informed consent form at Visit 0. At this visit, investigators should collect baseline data, including demographic data (gender, age, height, weight, education level and smoking history), history of asthma (disease duration, disease severity and exacerbation history), and past and concurrent medical conditions and medication (both asthma and non-asthma). ACT, AQLQ(S) and lung function test will be completed as the baseline measurement in sequence.
- Treatment period (week 0-week 24): a 24 week treatment period. Subsequent scheduled visits occur as follows: Week 4 (Visit 1), Week 8 (Visit 2), Week 12 (Visit 3), Week 16 (Visit 4), Week 20 (Visit 5) and Week 24 (Visit 6).
- In this cluster-randomization design, each study centre, considered as a cluster, will be randomized to either ACT guided treatment group or control group (usual care group). The randomization will be stratified according to the hospital level (Tier 3 vs. Tier 2). The hospital level is determined in accordance with the uniform requirements of the government. And a Tier 3 hospital is on a larger scale and provides superior medical care than a Tier 2 hospital.
- For the subjects who are recruited in the ACT centres, they will be treated based on the ACT score. For subjects who are recruited in the control centres, they will be treated based on doctor's subjective judgment.

Table 1 ACT-guided treatment

ACT score	Treatment adjustment
ACT=25, ≥ 3 months	Step-down treatment
ACT ≥ 20 , <25 or ACT=25, <3 months	No change

ACT score	Treatment adjustment
ACT \leq 19	Step-up treatment

- During the treatment period, subjects should fill in the paper diary record card (DRC) every morning and evening, record their morning and evening PEF, symptom and medication. At each visit, subjects should complete the ACT at clinic. For the ACT guided group, the ACT must be completed prior to any other assessments are conducted. For the control group, subjects should complete the ACT after investigator making the treatment decision. This will ensure the investigators make treatment decision based on his/her clinical judgement, not based on ACT. For the control group, all subsequent assessments should be conducted in the same order as the ACT guided group. Investigators will be responsible for checking the subjects' DRC, including symptom score and evaluating therapeutic compliance.

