7.3. Efficacy

7.3.1. Primary Endpoint (s)

- The primary endpoint for the study is the percentage of subjects who have an ACT score ≥ 20 or an improvement of more than 3 points in ACT during the 24-week treatment period.

Asthma control test (ACT)

ACT is a self-administered questionnaire comprising five questions [Nathan, 2004]. Each of the five items in the ACT is assessed on a five point scale and the scores are summed

to give a total score ranging from 5 to 25, with a score of ≥ 20 denoting 'well-controlled asthma', a score of 16-19 denoting 'not well-controlled asthma', and a score of ≤ 15 denoting 'very poorly controlled asthma'. The recall period of the questionnaire is four weeks. ACT must be completed by the subject at each visit. For the control group, subjects should complete the ACT after investigator making the treatment decision. Differences of 3 points in mean ACT scores between 2 groups or over time in an individual patient are clinically significant [Schatz, 2009]. An improvement of more than 3 points in ACT from baseline will also serve as primary endpoint.

The questionnaire will be attached separately.

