7.3.4. Guidance for Questionnaires Administration

All questionnaires in the study are self-administered. It is recommended that a subject completes all questionnaires before the physical examination and lung function. For the ACT guided group, the ACT should be completed first followed by the AQLQ (at visits during which the AQLQ is measured) and the treatment decision. The remaining assessments should be conducted after the AQLQ has been completed. This order should be used throughout the study. For the control group, the ACT must be completed after the treatment decision has been made, but the remaining assessments should be conducted in the same order as for the ACT guided group.

It is important that in the ACT guided group, the patients are blinded to the treatment decision to prevent any potential bias when the patients complete the AQLQ.

The following guidance is applicable to all questionnaires for the present study.

Subjects should be requested to perform the questionnaire as completely and accurately as possible. Regardless of when the questionnaire is completed, the subject should be given adequate time to complete all questions. No stated or implied time limit for completing the questionnaires should be given. The subject should be given a quiet area in which to complete the questionnaire.

If a subject has difficulty in completing the questionnaire, a third party (an investigator or study personnel) can help the subject to understand and answer the questions. If the subject should request help or clarification of any question in the questionnaire, the investigator or the study personnel is to instruct the subject to reread the instructions and to give the best answer possible to each question. The investigator or study personnel will not provide the subject with any possible answer to any question.

A subject may use a black or blue pen to complete the questionnaire. If the subject wishes to change a response, the original response should be crossed out with a single line, and then dated and initiated by the subject, as applicable and the alternative response should be marked. Once the subject returns the questionnaire to the investigator or the study personnel, no changes will be allowed except for incomplete items.

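### After baseline, the ACT and the Visit 6 AQLQ(S) are completed before the treatment decision in ACT centres but after it in control centres, a possible bias of unknown direction and size

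*Protocol*

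**What the plan says.** Protocol 4.2 sets the order for ACT centres: "For the ACT guided group, the ACT must be completed prior to any other assessments are conducted". For control centres it reverses the order relative to the decision, "For the control group, subjects should complete the ACT after investigator making the treatment decision", and gives the reason: "This will ensure the investigators make treatment decision based on his/her clinical judgement, not based on ACT".

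Section 7.3.1, which defines the primary endpoint, repeats the control rule: "ACT must be completed by the subject at each visit. For the control group, subjects should complete the ACT after investigator making the treatment decision". Section 7.3.4 repeats both halves, "For the ACT guided group, the ACT should be completed first followed by the AQLQ" and then the decision in ACT centres, against "For the control group, the ACT must be completed after the treatment decision has been made" in control centres. The remaining assessments follow in the same sequence in both arms, so in control centres the AQLQ(S) also comes after the decision.

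Section 7.3.4 adds that in the ACT-guided group it is important that "the patients are blinded to the treatment decision to prevent any potential bias when the patients complete the AQLQ". No matching sentence covers control patients, and none covers the ACT.

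SAP 7.1.1 counts a subject as a responder if the ACT total reaches 20, or rises by more than 3 points, at any one post-baseline assessment. Protocol 6.2 makes the study open-label.

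**The concern.** A questionnaire completed before the consultation and one completed after it are not taken under the same conditions. A control patient may already know whether treatment is being changed and may have just been reassured or alerted by the doctor. An ACT-arm patient has had neither experience. The protocol accepts in 7.3.4 that such knowledge could colour answers to the AQLQ.

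Every centre follows only one order, so any effect of order is inseparable from arm in the ACT and AQLQ(S) endpoints, including time to first response. The added analyses in SAP 7.1.3 (GEE, Week 12, Week 24, Weeks 16, 20 and 24 together, MMRM) all use the same ACT scores and cannot remove it. The any-visit rule gives a small shift six chances to create or remove a response.

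**Working it through.** **1. Order by arm, side by side**

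| | ACT centres | Control centres |
|---|---|---|
| ACT, Visits 1 to 6 | first, before the decision | after the decision |
| AQLQ(S), Visit 6 | after the ACT, before the decision | after the ACT, so after the decision |
| Patient unaware of the decision | required for the AQLQ | not required |
| FEV1, PEF, diary scores | do not depend on ACT order | do not depend on ACT order |

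**2. Visit 0.** Both arms need the ACT for eligibility (below 20 by Protocol 5.1, not below 12 by 5.2), and 4.2 lists it first among the baseline measurements. An undisturbed baseline is therefore plausible in control centres. However, 7.3.1 and 7.3.4 state the control order without exempting Visit 0, so this is not certain. It matters for step 4.

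**3. The plan's own figure, for scale.** Inputs from Protocol 9.2.1: 29% against 44%, ICC 0.01, 35 evaluable per centre, 6 centres per arm, 80% power, two-sided 0.05, 20% dropout.

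- n per arm = (1.96 + 0.842)² × (0.29×0.71 + 0.44×0.56) / 0.15² = 157.8
- Design effect = 1 + 34×0.01 = 1.34; 157.8 × 1.34 = 211.4 per arm, 422.9 in total (plan: 420)
- 422.9 / 0.8 = 528.6 (plan: 528)

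The sample size reproduces and is not in dispute. A common order would leave it unchanged.

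**4. How a shift in the score would reach the endpoint (assumed values throughout).** The simulation assumed a mean true score of 16 with SD 3, visit noise SD 1 to 2, drift of -2 to +2 points over 24 weeks, whole-point scores, baseline restricted to 12 to 19, and response at any of six visits.

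| Assumed shift in one arm | Change in any-visit response |
|---|---|
| 0.5 point at follow-up only | about 3 to 14 percentage points, mostly 7 to 11 |
| 1 point at follow-up only | about 5 to 27 percentage points |
| +0.5 point at follow-up and at Visit 0 | about 1 to 3 percentage points |

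The third row is small for a simple reason. From a baseline of 12 to 15, the first qualifying score is a gain of 4 (16 to 19), and a constant shift cancels out of a gain. From 17 to 19 the cut-off of 20 comes first, and only there does a constant shift still act.

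**5. What a shift in the response rate would do to the test (also assumed).** Effective n per arm = 210 / 1.34 = 156.7. Take no true effect, 29% in one arm and 29% + b in the other, with SE = √{[p(1-p) + q(1-q)] / 156.7}. For b = 5 points: SE = √[(0.2059 + 0.2244) / 156.7] = 0.0524; b/SE = 0.954; rejection probability = Φ(0.954 - 1.96) + Φ(-0.954 - 1.96) = 15.9%. For b of 2, 3 and 10 points it is 6.7%, 8.9% and 46.8%. A t reference with 10 df gives 13.9% at 5 points.

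Under the planned 44% against 29%, raising the control rate by 3 or 5 points cuts power from 79% to about 59% or 44%. Lowering it by 3 or 5 raises apparent power to about 92% or 97%. The same mechanism could favour either arm.

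**The case against.** The strongest defence is that the order is a considered trade-off. The comparator is care without the ACT, and 4.4 gives contamination as the reason for randomising centres. Five symptom questions just before the consultation could change what a control patient tells the doctor, and 2.2 names poor dialogue as part of the problem. It is only a partial answer that control patients already complete the ACT at every visit, because they now do so after the decision, about four weeks before the next one. This stands as a real cost of the remedy at Visits 1 to 5. It does not show that the present order is needed, since keeping the decision free of the ACT requires only that the investigator not see the form.

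The recall periods, four weeks for the ACT and two for the AQLQ, may also limit what a decision minutes earlier can do. That stands too, and the true shift could be near zero.

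Stronger readings are tempting but unsupported:

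- **That the protocol builds into its primary outcome the very bias it set out to prevent.** The safeguard in 7.3.4 names only the AQLQ; extending it to the ACT is a reasonable inference, not the protocol's statement.
- **That the artefact could rival the planned 15-point difference.** No document supports a 0.5- or 1-point order effect, and the larger figures need an unshifted baseline.
- **That the trial could not distinguish an artefact from benefit.** FEV1, PEF and diary scores do not depend on ACT order. They give supporting evidence, although they cannot correct the primary estimate.

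A common order would also leave another asymmetry: only in ACT centres do the patient's answers drive treatment changes.

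**Conclusion.** The point holds as a design weakness, not a slip. At post-baseline visits the primary outcome, and at Visit 6 the AQLQ(S), are taken before the decision in one arm and after it in the other. The resulting bias is possible, of unknown direction and size, and fully confounded with arm for endpoints built on those two questionnaires.

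The figures of 3 to 14 and 1 to 3 percentage points illustrate sensitivity under assumed score distributions and an assumed half-point shift; they do not estimate what will happen. Which range is relevant depends on whether the control-arm Visit 0 ACT is disturbed, and the documents leave that unclear. The documents also do not say whether a study treatment decision is made at Visit 6; if none is, the difference there reduces to whether the consultation comes first. The change is worth making because it is cheap and would align the timing of these measurements by arm.

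**What to change.** **Visit 6.** In both arms, have patients complete the ACT and then the AQLQ(S) on arrival, before any consultation or decision. There is no contamination cost, because no later study outcome follows. This protects only the AQLQ(S) and the Week 24 ACT analyses; five of the six visits that can trigger the primary response stay as they are.

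**Visits 1 to 5, to protect the any-visit primary endpoint.** Use the same arrival-first order for the ACT. In control centres, withhold the form from the treating investigator until the treatment decision is recorded. Section 7.3.4 currently lets the investigator help with questions and review completeness, so amend it to give those tasks to existing site staff other than the treating investigator.

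**Cost.** Wording changes in 4.2, 7.3.1 and 7.3.4, site instructions and a way to seal the form; no new staff, visits, assessments or subjects. The downside at Visits 1 to 5 is that completing the ACT first may prompt control patients to report symptoms and move usual care slightly towards the intervention. The sponsor should weigh that openly.

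**If recruitment has passed,** state the order difference as a limitation when interpreting the ACT and AQLQ(S) results, and read them beside FEV1, PEF and the diary scores.
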